1.6 Relapsed and/or Refractory Multiple Myeloma

The early development of ixazomib in patients with RRMM involves 2 studies (C16003 and C16004) with similar objectives, but each investigated 1 of the 2 dosing schedules commonly used with the first-in-class proteasome inhibitor, VELCADE.

Study C16003 is an open-label, dose escalation, phase 1 study of ixazomib dosing on a twice-weekly schedule on Days 1, 4, 8, and 11 of a 21-day cycle in adult patients with RRMM.(, 20, 21) Study C16004 is an open-label, dose escalation, phase 1 study of ixazomib dosing on a weekly schedule on Days 1, 8, and 15 of a 28-day cycle in adults patients with RRMM.(22, 23,

24) Both studies have now completed enrollment. The DLTs in Study C16003 were rash macular and thrombocytopenia and the DLTs in C16004 were nausea, diarrhea, vomiting, and erythema multiforme.

In the dose escalation component of both studies, patients had multiple myeloma that had relapsed following at least 2 lines of therapy that must have included bortezomib, thalidomide (or lenalidomide), and corticosteroids. In both studies, when the MTD was established, cohorts of patients representing the heterogeneous patient population currently seen in clinical practice were to be enrolled into 1 of 4 expansion cohorts, including a relapsed and refractory cohort, a carfilzomib cohort, a proteasome inhibitor-naïve cohort, and a VELCADE-relapsed cohort.

Final study results are currently being analyzed, but preliminary data suggest that ixazomib has anti-tumor activity in heavily pretreated MM patients, with durable responses/disease control, and is generally well tolerated. Please refer to the ixazomib IB and SMA for further information.

1.7 Newly Diagnosed Multiple Myeloma (NDMM)

Multiple research paths are being explored in patients with NDMM with a focus on evaluating ixazomib in combination with agents commonly used across treatment settings. The development of ixazomib in combination with lenalidomide with dexamethasone (LenDex) in patients with NDMM who are transplant eligible or ineligible involves 2 studies (C16005 and C16008) with similar study designs except for a few key differences, namely the schedules of ixazomib and dexamethasone. Ixazomib is also being evaluated in combination with melphalan and prednisone (MP) for patients who are not transplant eligible due to age or coexisting morbidity (in Study C16006).

All 3 studies are phase 1/2, with phase 1 focusing on safety and phase 2 on efficacy (and further characterization of safety). Please refer to the ixazomib IB and SMA for further information.

1.8 Clinical Trial Experience Using the Intravenous Formulation of Ixazomib

See the IB for descriptions of the 2 studies that investigated IV ixazomib in advanced solid tumors and advanced lymphoma (Studies C16001 and C16002, respectively).

1.9 Study Rationale

Glioblastoma, the most common primary tumor of the brain in adults, is rarely associated with cure or even control. Advances in surgical care and radiation planning have improved safety, and the addition of temozolomide to initial therapy has added some months to overall survival. At progression bevacizumab extends time to further imaging progression, but not overall

survival. Having said this, average overall survivals are still in the range of 12-14 months. This clearly leaves room for improvement by exploring other therapeutic modalities. Standard cytotoxic agents have been studied from a number of standpoints and their effect has probably been maximized.

Thus, alternative agents, either targeted to critical pathways related to tumor growth, or interrupting normal tumor cellular metabolism provide promising alternatives. One of these strategies is altering the normal function of the 20S proteasome subunit. Ixazomib has a shorter 20S proteasome dissociation half-life than bortezomib, which plays an important role in improving tissue distribution. Direct comparison with bortezomib has revealed that Ixazomib has an improved pharmacokinetic and pharmacodynamic profile and shows superior antitumor activity in both solid tumor and hematologic xenograft models, and shows antitumor activity when administered via multiple dosing routes and regimens. Although bortezomib has not been shown to have single agent efficacy in glioblastomas, the characteristics of ixazomib may be advantageous. It has not been determined as to whether or not the active metabolite of ixazomib reaches these tumors effectively. Preclinical models of glioblastoma, though very interesting, do not easily recapitulate the human situation in terms of size, tumor heterogeneity or effects of systemic metabolism. In order to address this question directly, a phase 0 study of ixazomib is proposed here to answer this question prior to moving forward with more advanced phase studies.

1.10 Potential Risks and Benefits

Please refer to the current ixazomib IB and SMA.

The clinical benefit of ixazomib continues to be studied in a comprehensive and global development plan that involves studies sponsored by Millennium. Ixazomib appears to show early signs of anti-tumor activity as evidenced by at least 50% reduction in disease burden in some patients, including patients that have been heavily pretreated as well as those with newly diagnosed MM, and prolongs stabilization of the underlying disease in other patients across all ongoing trials. The preliminary findings are favorable when considering historical and currently available therapies for the patient populations evaluated. Though additional data are needed to characterize the clinical benefit of this drug, the emerging data supports expanded development of ixazomib for the treatment of patients with advanced malignancy.

This study will be conducted in compliance with the protocol, good clinical practice (GCP), applicable regulatory requirements, and International Conference on Harmonisation (ICH) guidelines.

2. STUDY OBJECTIVES

2.1 Primary Objectives

1. Measurement of tissue concentration of ixazomib in a glioblastoma after preoperative administration
2. Measurement of blood and plasma concentration of ixazomib during surgical sampling after preoperative administration

2.2 Secondary Objectives

1. Assessment of the safety of MLN9708 after single dose administration in glioblastoma patients undergoing surgery for tissue concentration assessment.

3. STUDY ENDPOINTS

3.1 Primary Endpoints

Determination of brain tumor tissue, blood and plasma concentrations ixazomib

3.2 Secondary Endpoints

Determination of the safety of MLN9708 after single dose administration in glioblastoma patients undergoing tumor resection

4. STUDY DESIGN

4.1 Overview of Study Design

Individuals who are candidates for surgery for recurrent (or progressive) glioblastoma will be considered for participation in this study. Those deemed by the PI to be potential candidates will be counseled and provided a consent. Those signing a consent will then undergo eligibility screening. Those eligible will receive 4 mg of Ixazomib orally 3 hours prior to surgery and be on study as of that day. Tumor samples will be obtained at the time of surgery and provided to Covance for MLN2238 assay. Also during the surgery, blood samples will be obtained at the time of induction, one and two hours later and provided to Covance for ixazomib assay in both blood and plasma. At the time of return to the outpatient clinic the individual will be assessed for safetyrelated to Ixazomib administration. At that point the individual will be off study. Adverse events are followed and reported for 30 days after drug administration. The subject will continue to follow-up with their surgeon and oncologist as per standard care for their circumstance and therapy dictates and the adverse events will be captured at those follow-up visits.

4.2 Number of Patients

Three patients will be enrolled in this study. Enrollment will commence at the time of Ixazomib administration.

4.3 Duration of Study

This investigation will enroll approximately 1 patient every 2 months with completion expected 6 months after Winship Cancer Center checklists are completed. For the individuals enrolled, study activity will last from the day of surgery until the day the sutures or staples are removed. The average time period for the wound to heal well enough for suture or staple removal is 10-17 days depending on the nature of the surgical wound. (please note that all serious adverse events must be reported up to 30 days after the dose of ixazomib as described in Section 8.2: Procedures for Reporting Serious Adverse Events). The subject will continue to follow-up with their surgeon and oncologist as per standard care for their circumstance and therapy dictates and the adverse events will be captured at those follow-up visits.

4.4 Staggered Enrollment

Patients will be enrolled in a staggered fashion with ≥ 4 weeks between each patient dosed.

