7.1.7 Adverse Event Stopping Rule

For any toxicity \geq one grade above baseline for any pre-existing adverse events (AEs), and any new grade \geq 2 AEs study accrual will be suspended. The study team will review the data to determine the proper course of action. These actions may include further adverse event monitoring and evaluation to assess attribution of the adverse event observed, continued suspension of accrual pending study modification, dose modification, and closure of the trial.

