7.1.8 Data Safety Monitoring Plan

Winship Cancer Institute's Data and Safety Monitoring Committee (DSMC) will review toxicity and safety data for each subject following completion of the 2 week post-operative/off-study visit. The sponsor-investigator is responsible for providing adverse event data to the DSMC for review. Should any SAEs occur, from first dose of study drug through 30 days post-administration, the sponsor-investigator will halt enrollment and notify DSMC of event occurrence. Any SAE, regardless of relationship to the study drug, will be reported to the DSMC for review prior to enrollment of subsequent patients to evaluate the safety of trial continuation.

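### The four-week minimum between patients ends before the 30-day SAE halt window closes, and routine DSMC review need not precede the next dose

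*Combined protocol and SAP*

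**What the plan says.** Four sections govern when the next patient may be dosed.

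- **Section 4.4** sets the spacing: "Patients will be enrolled in a staggered fashion with ≥ 4 weeks between each patient dosed".
- **Section 4.2** defines the moment of enrollment: "Enrollment will commence at the time of Ixazomib administration". Halting enrollment therefore means withholding the next dose.
- **Section 7.1.8** contains two DSMC reviews. The routine one: the DSMC "will review toxicity and safety data for each subject following completion of the 2 week post-operative/off-study visit". The event-driven one: "Should any SAEs occur, from first dose of study drug through 30 days post-administration, the sponsor-investigator will halt enrollment and notify DSMC", followed by "Any SAE, regardless of relationship to the study drug, will be reported to the DSMC for review prior to enrollment of subsequent patients". Only the second is written as a precondition for the next patient.
- **Section 7.1.7** suspends accrual for any new adverse event of Grade 2 or higher, or a worsening of at least one grade in a pre-existing one. Then: "The study team will review the data to determine the proper course of action". The DSMC is not mentioned.

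On follow-up, Section 4.1 says: "Adverse events are followed and reported for 30 days after drug administration". The last scheduled study visit is suture or staple removal, 10 to 20 days after surgery (Section 6.11). Later events are picked up at standard-care visits (Sections 4.1, 4.3 and 6.11).

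**The concern.** With three patients dosed one at a time, staggering lets what happens to one patient inform the decision to dose the next. The plan sets its own horizon for that information: an SAE through day 30 is serious enough to stop the next dose until the DSMC has looked at it. The spacing rule lets the next dose go ahead before that horizon is reached.

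The second part is independent of the first. Where no SAE has been reported, nothing says the DSMC must have finished with one patient before the next is dosed. Section 8.1.2 states that a Grade 3 or 4 event need not be serious, so a severe but non-serious event could suspend accrual and be resolved without DSMC input.

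At stake is whether a patient can be exposed while the safety information that the plan itself treats as decisive is incomplete or has not been reviewed. No efficacy or concentration estimate is affected.

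**Working it through.** **The plan's own figure.** Sections 4.2 and 4.3: 3 patients × 2 months per patient = 6 months, which matches the stated duration. No power calculation is involved, because Section 7.1.1 bases the sample size on clinical judgment.

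**Interval against window.**
- Minimum interval (4.4): 4 × 7 = 28 days.
- SAE halt window (7.1.8): 30 days, the same length as adverse event follow-up in 4.1.
- Shortfall: 30 − 28 = 2 days for each consecutive pair of patients.

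**Scheduled observation.** Dosing is on the day of surgery, so the last visit is about day 10 to 20 after the dose.
- From that visit to the earliest next dose: 28 − 20 = 8 days to 28 − 10 = 18 days.
- From that visit to the end of the halt window: 30 − 20 = 10 days to 30 − 10 = 20 days, with no study contact scheduled.

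The 8 to 18 days is time available for routine DSMC review. The plan does not require the review to be finished in it, nor to include data from the later part of the window.

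**What the text does in each case, with the next patient dosed on day 28.**

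| Event in the previous patient | Effect on the next dose |
|---|---|
| SAE known before day 28 | Stopped until DSMC review (7.1.8) |
| SAE arising after that dose, through day 30 | Already given; later patients are halted |
| SAE arising before day 28 but recognised afterwards | Already given; later patients are halted |
| Non-serious event meeting 7.1.7, known before day 28 | Accrual suspended; the study team decides; DSMC clearance not required |
| No qualifying event | May go ahead whether or not routine DSMC review is complete |
| Previous patient dosed, then replaced before the off-study visit (6.12, 7.1.1) | Routine review follows completion of a visit that did not take place, so it has no stated trigger |

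On the last row, Section 6.12 does ask for end-of-study procedures at withdrawal, but it does not link them to DSMC review.

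**Room in the timetable.** Three patients give two intervals, barring replacements. The minimum span is 2 × 28 = 56 days. An interval equal to the window gives 2 × 30 = 60 days. If day 30 must be fully past, it is 2 × 31 = 62 days. Planned accrual gives 2 × 2 months, about 122 days.

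No probability is attached to the overlap, because the documents give neither the distribution of arrival times nor the timing of SAEs.

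**The case against.** The strongest reply is that the sections do not contradict each other. Section 7.1.8 says what happens when an SAE occurs. It does not say that 30 days must pass before the next dose, and Section 4.4 gives no purpose for the stagger. Both rules can be obeyed at once. That is right, and it rules out some stronger readings.

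- A reader might infer that the SAE halt does not work on days 29 and 30. It does work. It fails only for one next patient who has already been dosed, and it still protects everyone after that.
- A reader might turn 2 days out of 30 into about 7% of the risk. That is a share of calendar days. Nothing in the documents says that SAEs are spread evenly over the window.
- A reader might infer that patients have no independent oversight unless an SAE occurs. The DSMC reviews every subject, and nothing suggests that it would need more than the 8 to 18 days available.

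Existing safeguards also deserve weight. The trigger in Section 7.1.7 is sensitive: Grade 2 is enough, with no attribution requirement, so after a craniotomy accrual may often be suspended already. Each patient receives a single administration, and Section 1.3 cites preliminary clinical data on 653 patients, so this is not a first-in-human setting.

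These arguments limit the size of the problem but do not remove it. Planned accrual is an expectation, whereas Section 4.4 is the operative rule. The sensitive trigger acts only on events already observed, and the study team can lift the suspension.

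**Conclusion.** The point holds in limited form. Following the plan exactly, one next patient can be dosed before the previous patient's 30-day halt window has closed and before the DSMC has reviewed that patient. The nominal overlap is 2 days per interval. Late recognition can extend the affected period back towards the last scheduled visit, because no study contact is scheduled after day 10 to 20.

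Of the two parts, the missing link between routine DSMC review and the next dose is the more substantive, since it does not depend on dosing at exactly the minimum interval.

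Practical exposure is small: four weeks is a minimum, the planned spacing is about two months, and known SAEs and qualifying adverse events already stop accrual. The conclusion rests on reading enrollment as dosing (4.2) and on counting the window from the dose (7.1.8). The correction is worth making because it concerns patient safety and costs very little. The documents do not support a claim that the plan is unsafe or that the halt is inoperative.

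**What to change.** Reconcile Sections 4.4, 7.1.7 and 7.1.8 on three matters:

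1. **Interval and window.** The minimum spacing in 4.4 should be no shorter than the SAE window that the plan itself sets in 7.1.8.
2. **Timing and content of DSMC review.** State that review of the previous dosed patient is complete before the next is dosed, and that it covers the whole window. A review closed on data from the day 10 to 20 visit alone would not achieve this. Include patients who are replaced or who miss the off-study visit.
3. **Lifting a suspension.** State who clears resumption of accrual after a 7.1.7 suspension, and whether the DSMC has a part in it.

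The cost is a few sentences in an amendment. Across two intervals the minimum span grows by 4 to 6 days (60 − 56 to 62 − 56), against about 122 days at planned accrual, so the 6-month duration need not change. The DSMC already reviews each subject, so the change is that its review must cover the full window and be finished before the next dose. Sample size and analysis are unaffected.

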5. STUDY POPULATION

5.1 Inclusion Criteria

Each patient must meet all of the following inclusion criteria to be enrolled in the study:

1. Male or female patients 18 years or older.
2. Voluntary written consent must be given before performance of any study related procedure not part of standard medical care, with the understanding that consent may be withdrawn by the patient at any time without prejudice to future medical care.
3. Female patients who:
 - Are postmenopausal for at least 1 year before the screening visit, OR
 - Are surgically sterile, OR
 - If they are of childbearing potential, agree to practice 2 effective methods of contraception, at the same time, from the time of signing the informed consent form through 90 days after the last dose of study drug, OR
 - Agree to practice true abstinence when this is in line with the preferred and usual

lifestyle of the subject. (Periodic abstinence [eg, calendar, ovulation, symptothermal, post-ovulation methods] and withdrawal are not acceptable methods of contraception.)

Male patients, even if surgically sterilized (ie, status post-vasectomy), must agree to one of the following:

- Agree to practice effective barrier contraception during the entire study treatment period and through 90 days after the last dose of study drug, OR
 - Agree to practice true abstinence when this is in line with the preferred and usual lifestyle of the subject. (Periodic abstinence (eg, calendar, ovulation, symptothermal, post-ovulation methods] and withdrawal are not acceptable methods of contraception.)
4. Patients must have a previous diagnosis of a recurrent or progressive glioblastoma for which surgical resection is now indicated.
 5. Eastern Cooperative Oncology Group (ECOG) performance status and/or other performance status 0, 1, or 2 or (Karnofsky Performance Status of 60 or above).
 6. Patients must meet the following clinical laboratory criteria:
 - Absolute neutrophil count (ANC) $\geq 1,500/\text{mm}^3$ and platelet count $\geq 100,000/\text{mm}^3$. Platelet transfusions to help patients meet eligibility criteria are not allowed within 3 days before study enrollment.
 - Hemoglobin > 9 g/dL
 - Total bilirubin $\leq 1.5 \times$ the upper limit of the normal range (ULN).
 - Alanine aminotransferase (ALT) and aspartate aminotransferase (AST) $\leq 3 \times$ ULN for the lab utilized.
 - Creatinine ≤ 1.5 mg/dL
 - Calculated creatinine clearance ≥ 30 mL/min (see Section 11.2).

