6.2 Study Drug Administration

Ixazomib Administration

All protocol-specific criteria for administration of study drug must be met and documented before drug administration. Study drug will be administered or dispensed only to eligible patients under the supervision of the investigator or identified subinvestigator(s). Patients should be monitored for toxicity, as necessary, and doses of ixazomib should be modified as needed to accommodate patient tolerance to treatment; this may include symptomatic treatment, dose interruptions, and adjustments of ixazomib dose (see Section 6.3).

Capsules of ixazomib will also be referred to as study drug. Study drug will be supplied by Millennium as capsules of 0.2-, 0.5-, and 2.0 mg, or as capsules of 2.3-, 3.0- and 4.0 mg ixazomib.

The prescribed administration of the ixazomib dose in this study is one 4.0 mg dose approximately 3 hours prior to surgery. No further doses of ixazomib will be administered. The dose will be dispensed by the Emory University Hospital Research Pharmacy and administered by the PI who will document the time of administration, the dose, and toleration of the dose in the operative dictation. The patient will be in the preoperative waiting room and then the preoperative holding area after administration while being prepared for surgery. As there is only one dose used in this study, and it will be documented as part of the surgical procedure, no drug diary will be used.

Patients will be instructed to swallow ixazomib capsules whole, with water, and not to break, chew, or open the capsules. Study drug should be taken on an empty stomach (no food or drink) as they will have been NPO since midnight on the day surgery in preparation for general anesthesia. Each capsule should be swallowed separately with a sip of water. A total of approximately 8 ounces (240 mL) of water should be taken with the capsules.

Ixazomib Destruction

Investigational ixazomib (expired or end of study) should be destroyed on site according to the institution's standard operating procedure. Be sure to document removal and destruction on drug accountability logs.

Anesthetic agents, corticosteroids, anticonvulsants, antibiotics and other supportive agents will be administered during and after the surgical procedure (respecting those not allowed in the exclusion criteria list item number 8 above).

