6.11 Study Treatment

Schedule of Events and Observations

	Consent	Screening	Ixazomib Administration 3 Hours Before Surgery	Surgery	Postop Day 1	Postop Visit for Staple/Suture Removal
Reference Time Line	14 or fewer days before date of surgery	After consent and prior to ixazomib administration	1 to 3 hours prior to surgical incision	On average a two to four hour period of time with sampling occurring as clinically safe during the tumor resection	Assessment 12 to 36 hours after the end of the surgery	Depending on the nature of the wound repair and integrity staple/suture removal will occur 10 to 20 days after the day of surgery
Patient Education	x					
Laboratory screening		x				
Observation for clinical and laboratory toxicity using standard postop parameters*			x		x	x
Blood sampling just prior to incision				x		
Blood sampling during tumor sampling				x		
Blood sampling during surgical closure				x		
Tumor sampling				x		
* Toxicities are to be assessed according to the NCI Common Terminology Criteria for Adverse Events (CTCAE), version 4.03.						

Informed Consent Process: Patients with recurrent glioblastoma who need surgery will be presented the concept of this study and its pro's and con's. They will then receive a consent form and be allowed to review it. They will then be allowed to ask questions and provided these are satisfactorily answered sign consent. This process may take one or more days.

Screening: After signing informed consent there will be determination of performance status, CBC, Complete Metabolic Panel, Na/K/Glucose/Chloride/Bun/Cr, PT/PTT/INR, Urinalysis, & Serum pregnancy test.

Ixazomib Administration: 4.0 mg Ixazomib administration orally with 8 oz of water 3 hours prior to projected surgery start time. The individual will be observed for evidence of treatment-emergent adverse events. This will be recorded as the on study time. Accurate recording of the time of ixazomib administration will be made in the patient's clinical records.

Surgery: One red top tube of blood will be collected at the time of surgical incision, tumor sampling and wound closure. The time of each sampling will be recorded. The tumor will be sampled at three different sites and the timing of the sampling will be recorded.

Post Op Day 1: General and neurologic exam observations will be collected and laboratory evaluations performed will be collected and recorded.

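### The platelet-transfusion bar counts back from dosing, not from the qualifying count, so a transfusion-supported count can qualify a patient

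*Combined protocol and SAP*

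**What the plan says.** Section 5.1 item 6 sets a platelet floor of 100,000/mm³ and adds: "Platelet transfusions to help patients meet eligibility criteria are not allowed within 3 days before study enrollment". Section 4.2 fixes the reference point: "Enrollment will commence at the time of Ixazomib administration". Section 4.1 agrees: "Those eligible will receive 4 mg of Ixazomib orally 3 hours prior to surgery and be on study as of that day". Section 6.11 also treats the time of dosing as the on-study time.

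The schedule table appears in the protocol summary and again in 6.11. In both, consent is "14 or fewer days before date of surgery" and laboratory screening is "After consent and prior to ixazomib administration". The 6.11 text names the tests once: "After signing informed consent there will be determination of performance status, CBC, Complete Metabolic Panel", followed by further panels. No section sets a maximum age for the count, asks for a repeat count before dosing, or sets an interval between transfusion and count.

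Section 6.2 adds a general check: "All protocol-specific criteria for administration of study drug must be met and documented before drug administration". Section 7.1.7 (accrual suspension) and section 8.1.1 (when a laboratory value is an adverse event) both refer to baseline. Neither defines it.

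**The concern.** The wording of the transfusion rule shows its purpose: a transfusion should not produce the count that makes a patient eligible. That purpose depends on the interval between transfusion and count. The rule instead controls the interval between transfusion and dosing, and the count may precede dosing by up to two weeks.

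Two things are at stake. First, a patient whose platelets may by then be under the protocol's own floor could be dosed on the day of a craniotomy with a drug that section 6.6 associates with thrombocytopenia. Second, screening is the only pre-dose laboratory panel that the protocol names. A transfusion-supported count could therefore become the value against which later platelet changes are judged, in a safety data set of three patients.

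**Working it through.** No sample size, power or event figure depends on this point, and the plan states no figure to reproduce. The check is a count of calendar days.

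**Inputs**
- Day 0 is dosing (4.1), which is also enrollment (4.2) and the day of surgery.
- Restriction: 3 days back from enrollment (5.1 item 6).
- Earliest consent: day −14 (schedule tables).
- Screening CBC: any time after consent and before dosing (schedule tables).
- Assumption: the CBC may be drawn on the day of consent, and whole days are counted.

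Let *c* be the day of the qualifying count and *t* the day of the transfusion, with *t* ≤ *c*. Then *c* runs from −14 to 0, which gives 14 + 1 = 15 possible count days. As written, a transfusion is barred only if *t* ≥ −3.

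**Same-day transfusion (*t* = *c*).** Permitted when *c* ≤ −4, that is, days −14 to −4: 14 − 4 + 1 = 11 of 15.

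**Transfusion 3 days or less before the count (*c* − 3 ≤ *t* ≤ *c*).** Some permitted *t* exists when *c* − 3 ≤ −4, so *c* ≤ −1, that is, days −14 to −1: 14 of 15.

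**Reading of the boundary.** If a transfusion exactly on day −3 counts as allowed, the conditions become *c* ≤ −3 and *c* ≤ 0, giving 12 of 15 and 15 of 15.

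**Shorter consent-to-surgery interval.** If consent falls on day −*k* (*k* ≥ 1), the two figures are max(*k* − 3, 0) of *k* + 1 and *k* of *k* + 1. With *k* = 14 these return 11 of 15 and 14 of 15. The same-day route closes only when the count cannot be drawn before day −3. The second route stays open for any count drawn before day 0.

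**Example.** Transfusion on day −10, CBC at or above the floor on day −9, dosing on day 0. The transfusion is 10 days before enrollment, so it is not barred. It is 1 day before the count, which qualifies. The count is 9 days old at dosing.

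**Same 3 days counted back from the CBC (illustration only).** Every *t* from *c* − 3 to *c* is barred, so the second figure falls from 14 of 15 to 0 of 15.

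These are counts of permitted calendar combinations, not probabilities.

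**The case against.** The strongest reply is that the platelet floor itself applies at enrollment. Section 5.1 requires every criterion to be met for a patient to be enrolled, enrollment is dosing, and 6.2 requires the criteria to be met and documented first. On that reading, a patient below the floor on day 0 is simply ineligible. This is right about intent, and it means the gap is one of verification. It does not close the gap, because neither section asks for a recount and an earlier screening value satisfies the documentation.

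Section 5.2 exclusion 2 removes patients who have not recovered to Grade 1 or below from reversible effects of prior chemotherapy, a plausible reason for needing platelets. That lowers the risk, but it sets no washout interval and does not address the timing of the count. The toxicity row in the schedule is marked in the dosing column, but the text for that step names no laboratory draw.

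It is also true that if the qualifying CBC were always the last draw before dosing, counting back from enrollment or from the CBC would be nearly the same. The protocol does not require that.

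Several stronger readings are tempting and not supported:
- A reader might subtract 3 from 14 and call the remaining 11 days between count and dosing unprotected. Transfusions after the count cannot have raised it, so that interval is the wrong one. The 11 count days in the working are a different quantity.
- A reader might size the problem with the thrombocytopenia frequency in Table 1-2. That table pools multi-dose studies, single-agent and combination, and says nothing about transfusion before screening.
- A reader might conclude that the inflated count is the baseline and that a later fall will be attributed to ixazomib. Baseline is undefined, and the schedule of events, 7.1.6 and 7.1.7 all provide for attribution to be assessed.
- A reader might extend the point to chemistry and the pregnancy test. The transfusion rule does not bear on those, and exclusion 1 expressly accepts a pregnancy test from the screening period.

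**Conclusion.** The point holds as a mis-anchored eligibility rule. As written, a transfusion shortly before the qualifying count is compatible with the stated timing rules on most possible count days: 11 of 15 for a same-day transfusion and 14 of 15 for one within the preceding 3 days. A transfusion-supported count can therefore qualify a patient whose platelets may be below the floor at dosing. The same count could serve as baseline, in which case a later fall may be misread until attribution is reviewed.

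This rests on taking 4.2 literally, on the full 14-day window being used, and on no unwritten preoperative recount serving as the eligibility test. The documents do not say how often candidates receive platelets, so the number of patients affected cannot be estimated. The effect is confined to eligibility and the reading of platelet changes in three patients. The primary concentration endpoint and the planned summaries of drug concentration are untouched. It is worth correcting because the rule does not do what it was written to do.

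**What to change.** Reconcile 4.2, 5.1 item 6 and both copies of the schedule table so that the transfusion-free period and the platelet floor refer to the same identified pre-dose CBC. Count the transfusion restriction back from that CBC, and state how old it may be at dosing. Both parts are needed: re-anchoring alone still allows an old count, and an age limit alone leaves the transfusion-to-count interval unstated. The investigators set the length of each interval.

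In 7.1.7 and 8.1.1, name that CBC as the platelet baseline.

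The cost is about a sentence in 5.1, a schedule footnote, a short definition of baseline, and an occasional late screen failure.
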